# 7.4.1 Completed Study

The study enrolment will be considered as completed when the desired number of at least 33 included patients is reached. Patients completing the Wash-out Phase at the time the desired

IKERVIS®	
Study NVG16E128	Page 33 of 93
Protocol Version 4.0	23 March 2018

number of 33 included patients is achieved are eligible for inclusion if they fulfil the inclusion/exclusion criteria at the Baseline Visits.

The 3-Month open-label study treatment period will be completed when all included patients complete the assessments of the Month 3 Visit in accordance with the study protocol.

## 7.5 **Procedures for Discontinuation or Withdrawal of a Patient**

The investigator may terminate a patient's study participation at any time during the study when the patient meets the study termination criteria described in Section 7.3.2. In addition, a patient may discontinue his or her participation without giving a reason at any time during the study. Should a patient's participation be discontinued, the primary criterion for termination must be recorded. In addition, efforts should be made to perform all procedures scheduled for the Month 3/Early Termination (ET). Discontinued patients will not be replaced. Patients discontinued for AE(s) will be followed-up after patient's discontinuation until the event is resolved or considered medically stable by the investigator. In case of a patient lost-to-follow-up, the investigator must do his best to contact the patient initially by phone, then by letter, and finally by certified mail. If no response is obtained from the patient, the investigator is encouraged to contact one of the patient's relatives or his/her general physician. The evidence of these contacts must be recorded in the patient medical chart.

IKERVIS®	
Study NVG16E128	Page 34 of 93
Protocol Version 4.0	23 March 2018

#### 8.0 CLINICAL TRIAL MATERIAL MANAGEMENT

This section contains information regarding all medication and materials provided directly by the sponsor, and/or sourced by other means, that are required by the study protocol, including important sections describing the management of clinical trial material.

#### 8.1 Study Medication and Materials

#### 8.1.1 Dosage Form, Manufacturing, Packaging, and Labeling

#### 8.1.1.1 Investigational Drug

IKERVIS® is a sterile, ophthalmic cationic oil-in-water emulsion containing 1 mg/ml CsA.

IKERVIS®, which was granted an European Marketing Authorization by the European Commission in 2015, contains the following excipients:

- Medium Chain Triglycerides (MCT): the emulsion's oily agent that constitutes the main droplet core component and solubilizes the drug.
- Cetalkonium chloride (CKC): a cationic surfactant that provides an efficient emulsification and a long-term stability by providing positive charges to the oil droplets which are stabilized by electrostatic repulsion. Positively-charged oily droplets are also electro-statically attracted to the membranes of the ocular surface epithelial cells that are negatively-charged.
- Tyloxapol (octyl phenol polyxyethylene) and poloxamer 188 (polyethylene oxide (PEO), polypropylene oxide (PPO) triblock copolymer): two non-ionic surfactants which ensure the emulsification by reducing the interfacial tension between the aqueous and the oily phases.
- Glycerol: a polyhydric alcohol used as tonicity agent in ophthalmic preparations. Glycerol is added in an appropriate quantity to adjust the osmolality of the emulsion.
- NaOH: used as a pH adjuster.
- Water: as diluents and the main emulsion component.

Batch number and expiration dates will be provided in the certificate of analysis.

## 8.1.1.2 Washout Medication

Unpreserved artificial tears will be provided to the patient during the wash-out phase to use as needed to ameliorate their symptoms of DED. Bottles of the unpreserved artificial tears (sodium chloride 0.9%, Larmabak®, Laboratoire Théa France) will be dispensed in the French commercial packaging.

IKERVIS®	
Study NVG16E128	Page 35 of 93
Protocol Version 4.0	23 March 2018

# 8.1.1.3 Packaging and Labeling

IKERVIS® will be supplied in polyethylene single-dose containers presented in sealed laminate aluminum pouch package (1 pouch contains 5 single-dose containers).

8 aluminum pouches (i.e. 40 single-dose containers) of IKERVIS® will be placed together in a sealed cardboard box. One identical box will be dispensed for each of the three treatment phases: D0-M1 (Day 1 - Month 1), M1-M2 (Month 1 - Month 2) and M2-M3 (Month 2 - Month 3).

Each single dose container, aluminum pouch and sealed cardboard will carry an investigational label, indicating that the content is intended for investigational use only.

In addition, each cardboard box will carry a label bearing the protocol and treatment numbers.

## 8.1.2 Storage

All clinical trial material must be kept in an appropriate, limited-access, secure location until it is used or returned to the sponsor or designee for destruction. All study medication must be stored under the conditions specified on the label, and remain in the original container until dispensed. A daily temperature log of the drug storage area must be maintained every working day. The study medication and unpreserved artificial tears will be delivered to the study centres by the clinical supplies distributor. The study medication must be stored between 15 and 25°C. Initially each centre will receive adequate supplies (study medication and unpreserved artificial tears) to cover the study treatment period for a pre-defined number of patients. Additional supplies will be dispatched after taking into account the recruitment rate of each study centre. The investigator or his/her designee will be responsible for correct handling and storage of the study medication and unpreserved artificial tears during the course of the study.

## 8.1.3 Patient Identification

In order to ensure patient anonymity, patients will be identified by codes or other means of record identification, e.g.: 2 digits for site number, 2 digits for patient number by chronological order of entry in the study.

## 8.1.4 Dose and Regimen

During the 3-month study unpreserved artificial tears and the study medication must be dispensed only to study patients in accordance with the study protocol:

• At the Screening Visit each patient will be dispensed unpreserved artificial tears for use during the 2-week wash-out phase.

• At the Baseline Visit (on Day 1), after the validation of all inclusion and exclusion criteria, each eligible patient will be given unpreserved artificial tears and one sealed cardboard box containing enough study medication for the period Day 1 - Month 1.

• At Month 1 Visit, each patient will be given unpreserved artificial tears and one sealed cardboard box containing enough treatment for the period Month 1 - Month 2.
IKERVIS®	
Study NVG16E128	Page 36 of 93
Protocol Version 4.0	23 March 2018

• At Month 2 Visit, each patient will be given unpreserved artificial tears and another sealed cardboard box containing enough treatment for the period Month 2 – Month 3.

At Screening Visit, each patient will be instructed to instil with unpreserved artificial tears up to eight times per day in each eye for the relief of their symptoms of DED, during the 3-month study treatment period. At the following visits, their compliance will be checked, and they will be instructed to pursue the use of unpreserved artificial tears according to their DED symptoms within the protocol limits.

At Baseline Visit (Day 1), each patient will be instructed to instil one drop of study medication (IKERVIS®, 1mg/ml ciclosporin) into the lower conjunctival sac of each eye once daily at bedtime during the 3-month study treatment period. Each single-unit container of study medication yields two drops of study medication (one drop for instillation in each eye) and will be used only once. At the following visits, their compliance will be checked, and they will be instructed to pursue the treatment with IKERVIS® with the same regimen.

Changes in the IKERVIS® regimen during the study are not permitted.

## 8.1.5 Accountability

The study medication and sponsor provided unpreserved artificial tears are to be dispensed only by the investigator or designee, and will be used in accordance with this protocol. Under no circumstances will the investigator allow the study products to be used other than directed by the protocol. All dispensations and returns of study medication have to be documented in the investigator's file provided by the Sponsor.

Patients will be instructed to keep all unused and used containers and will be required to bring study medication containers to each clinic visit, regardless of whether the study medication container is empty. The destruction of the used and unused containers of study medication will be performed according to the instructions of the clinical monitor and has to be documented.

Upon completion or earlier termination of the study the investigator will, unless otherwise agreed, return to the clinical supplies distributor any surplus quantities, used and unused containers/bottles, of study medication or unpreserved artificial tears. The investigator will record each quantity of study medication or unpreserved artificial tears that has been damaged or is missing.

## 8.2 **Patient's Compliance**

Patient compliance will be assessed at each visit by the number of used and not used single-dose containers of study medication in relationship to the duration of the follow-up interval. All reported incidents of non-compliance and poor compliance will be recorded on the eCRF with the reasons. If a patient is persistently noncompliant with the study medication, the patient might be withdrawn from the study. All patients should be reinstructed about the dosing requirement during study visits. The authorized study personnel conducting the re-education must document the process in the patient source records.

IKERVIS®	
Study NVG16E128	Page 37 of 93
Protocol Version 4.0	23 March 2018

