## 7.4 Criteria for Discontinuation or Withdrawal of a Patient

The primary reason for discontinuation or withdrawal of the patient from the study should be recorded in the case report form (eCRF) using the following categories. For screen failure patients, refer to Section 9.1.9.

- 1. Adverse event (AE). The patient has experienced an AE that requires early termination because continued participation imposes an unacceptable risk to the patient's health or the patient is unwilling to continue because of an AE.
- 2. Protocol deviation. The discovery after administration of the first dose of study drug that the patient failed to meet protocol entry criteria or did not adhere to protocol requirements, and continued participation poses an unacceptable risk to the patient's health.
- 3. Lost to follow-up. The patient did not return to the clinic and attempts to contact the patient were unsuccessful. Attempts to contact the patient must be documented.
- 4. Voluntary withdrawal. The patient (or patient's legally acceptable representative) wishes to withdraw from the study. The reason for withdrawal, if provided, should be recorded in the eCRF.

Note: All attempts should be made to determine the underlying reason for the withdrawal and, where possible, the primary underlying reason should be recorded (i.e., withdrawal due to an AE should not be recorded in the "voluntary withdrawal" category).

- 5. Study termination. The sponsor, IRB, IEC, or regulatory agency terminates the study.
- 6. Lack of efficacy: the patient or the physician does not feel that the study medication has adequately relieved his/her symptoms.
- 7. Pregnancy. The patient is found to be pregnant.

Note: If the patient is found to be pregnant, the patient must be withdrawn immediately. The procedure is described in Section 9.1.8.

- 8. Investigator decision due to non-compliance (to IMP, study visits or study related procedure)
- 9. Other reason, specify.

Note: All attempts should be made to determine the reason if Other (e.g. moving...).

Note: The specific reasons should be recorded in the "specify" field of the eCRF.

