## 9.3.3 Unscheduled Visit/Premature Discontinuation

An unscheduled visit may be performed as needed between two scheduled visits. The reason for the visit will be recorded on the eCRF. The examinations required at an unscheduled visit will be at the discretion of the investigator.

If necessary, (e.g. to follow up an AE), the investigator may schedule further "unscheduled" visits at his/her discretion. Data from an unscheduled visit will not be collected in the eCRF with the exception of information related to an AE or the follow-up of an AE.

In case of premature study discontinuation between two scheduled visits, the Unscheduled Visit Form and the Exit Forms will be completed. If the premature discontinuation occurs during an Unscheduled Visit prior to Month 3, the investigator will complete and record all of the exams scheduled at the Month 3 Visit on the Unscheduled Visit Form. In case of premature study discontinuation, the investigator will ensure that all used and unused study medication for the study period has been collected from the patient.

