6.2 Handling of Missing Data

6.2.1 Efficacy Endpoints

Missing observations on CFS, VMR, and variance of OSI will be imputed by the last-observation-carried-forward (LOCF) approach.

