7.3 Medical and Surgical History

The medical and surgical history (i.e., medical events) will be coded using MedDRA (version v19.1 English, March 2016) and summarized for the FAS population. Each medical event will be classified into a system organ class (SOC) and mapped to a preferred term (PT). Any subject with more than one medical and/or surgical term within the same SOC or mapped to the same PT will be counted only once for that SOC or PT.

7.4 **Protocol Deviations**

In this study, protocol deviations are categorized as follows:

- Safety issues
 - Study drug storage condition outside of the protocol-defined condition

- Consent issues
 - Informed consent not signed
 - Informed consent data missing or not available
- Enrollment issues
 - Ineligible subject enrolled
- Protocol implementation issues
 - Visit out of window
 - Protocol-required exam(s) not done or missing
 - Administered rescue medication/therapy
 - Used prohibited medications/therapy
 - Non-compliance (compliance rate < 80%)
- Other

A protocol deviation is considered major if it may affect the subject's rights, safety, or wellbeing and/or the completeness, accuracy, and reliability of the study data. Santen's study team will review all protocol deviations and determine the list of major protocol deviations prior to database lock. FAS subjects with any major protocol deviation(s) will be tabulated by deviation category. In addition, protocol deviation(s) will also be listed.

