8.1.1 Primary Analyses of the Primary Endpoints

Spearman's coefficient of correlation and its 95% confidence interval will be calculated at Month 3 between the change from baseline of CFS and, respectively, the change from baseline of VRM and the change from baseline of variance of OSI.

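### Study withdrawal for persistent non-compliance can replace a valid Month 3 pair with an earlier one carried forward, and removes the patient from the observed-only and per-protocol repeats

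*Protocol*

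**What the plan says.** Protocol 8.2 states: "If a patient is persistently noncompliant with the study medication, the patient might be withdrawn from the study". Section 9.2 has the same sentence. Protocol 7.4 lists as discontinuation reason 8: "Investigator decision due to non-compliance (to IMP, study visits or study related procedure". Neither 8.2 nor 9.2 defines persistent non-compliance, and neither provides for a patient who doses poorly but continues to be assessed. Section 7.5 adds: "Discontinued patients will not be replaced".

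The protocol does ask for exit data. Section 7.5 says that "efforts should be made to perform all procedures scheduled for the Month 3/Early Termination (ET", and 9.3.3 says that, when discontinuation happens at an unscheduled visit before Month 3, "the investigator will complete and record all of the exams scheduled at the Month 3 Visit on the Unscheduled Visit Form".

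In the SAP, the primary analysis (8.1.1) is: "Spearman's coefficient of correlation and its 95% confidence interval will be calculated at Month 3". It relates change in CFS to change in VMR and to change in variance of OSI. The full analysis set (5.1) needs one dose and sets no compliance condition. For gaps, SAP 6.2.1 says: "Missing observations on CFS, VMR, and variance of OSI will be imputed by the last-observation-carried-forward (LOCF) approach". SAP 8.1.2 repeats the primary analyses on observed data only and on the per-protocol population, and adds a mixed model on observed cases. SAP 5.3 excludes from per-protocol anyone without the Month 3 measures. SAP 7.4 already lists "Non-compliance (compliance rate < 80" per cent) as a deviation category.

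**The concern.** The primary endpoints are within-patient correlations at Month 3. They do not compare arms or doses. A patient who skipped doses but attends at Day 84 supplies a CFS change and a vision change that belong in the analysis as much as anyone else's. Ending that patient's participation gives up the Day 84 result, and the analysis gains nothing, because the SAP already has a way to record poor compliance and a per-protocol repeat.

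The decision is also left to an unmasked investigator (SAP 3.2) who sees CFS and vision results at each visit. Who is withdrawn, and when, could therefore depend on response or on site. The documents do not show that it does, but the rule leaves room for it. Patients are not replaced, and SAP 3.1 reports 17 enrolled against 33 planned.

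**Working it through.** **Step 1. The plan's own figure.** There is no precision calculation and no dropout rate to reproduce. The nearest figure is 33 enrolled to obtain 30, an implied loss of 1 − 30/33 = 9.1%. The protocol summary calls the 30 included and SAP 3.3 calls them completed, so on the protocol's wording the margin does not cover later withdrawals.

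**Step 2. Where an exit exam lands.** SAP 4.1.5 maps measurements by study day.

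- Day 77 to 104: Month 3. Nothing is lost.
- Day 49 to 76: Month 2. Day 21 to 48: Month 1. Month 3 is missing and LOCF fills it from the earlier result.
- Before Day 21: no analysis window. The SAP does not say whether baseline, with a change of zero, may then be carried forward.

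Compliance is checked at each visit (Protocol 8.2), so a withdrawal on these grounds would naturally fall at or around Month 1 or Month 2.

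**Step 3. Which analyses change for an exit before Day 77.**

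- Primary, full analysis set with LOCF: patient kept, pair is early.
- Observed-only repeat: no Month 3 pair, patient absent.
- Per-protocol repeat: patient excluded under SAP 5.3.
- Mixed model on observed cases: Month 1 and Month 2 data still used.

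**Step 4. Precision in the repeats that lose the pair.** The approximate 95% limits are tanh(atanh(r) ± 1.96/√(n − 3)). The documents give no expected r, so an absolute value of 0.5 is assumed, with atanh(0.5) = 0.549. For n = 17, 1.96/√14 = 0.524, giving tanh(0.025) to tanh(1.073). Widths are taken before rounding the limits.

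| Pairs | 95% limits | Width |
|---|---|---|
| 30 | 0.17 to 0.73 | 0.56 |
| 17 | 0.03 to 0.79 | 0.77 |
| 16 | 0.01 to 0.80 | 0.79 |
| 15 | −0.02 to 0.81 | 0.82 |
| 14 | −0.04 to 0.81 | 0.86 |

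Each lost pair costs about 0.02 to 0.04 of width. With the standard error √((1 + r²/2)/(n − 3)), often used for Spearman's coefficient, the widths for 17 to 14 pairs are 0.81, 0.84, 0.87 and 0.90. From 17 to 14 pairs, on the first formula, the width goes from 0.89 to 0.99 at an assumed 0.3 and from 0.55 to 0.63 at 0.7.

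**Step 5. Is the range of CFS change cut?** The documents give no outcome for poor compliers. The nearest proxy is vehicle in the two earlier trials (Protocol 4.1.3). The differences in mean CFS change at Month 6 are 1.81 − 1.48 = 0.33 and 1.05 − 0.82 = 0.23 grade. A simulation with 17 patients, 1 to 3 of them withdrawn, used these assumptions, none of which is in the documents: latent correlation −0.5, mean CFS change −1.5, SD 1.0 or 1.3 before grading, half of the mean change reached at exit, and within-patient correlation 0.6. The table shows 3 withdrawn and SD 1.0.

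| Shift in non-compliers | Handling | SD of CFS change | Mean Spearman r |
|---|---|---|---|
| 0.33 grade | All followed | 1.008 | −0.458 |
| 0.33 grade | Pairs dropped | 0.996 | −0.450 |
| 0.33 grade | Early pair carried | 1.054 | −0.477 |
| 1.5 grades (no improvement) | All followed | 1.138 | −0.506 |
| 1.5 grades (no improvement) | Pairs dropped | 0.997 | −0.445 |
| 1.5 grades (no improvement) | Early pair carried | 1.133 | −0.501 |

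With the vehicle-like shift, dropping pairs changes SD and r by about 0.01 at most, and carrying the early pair forward slightly raises the SD. A visible fall needs no improvement at all plus deletion of the pairs, and LOCF almost removes it.

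**The case against.** The rule is narrow: withdrawal is optional, the non-compliance must be persistent, and patients are to be reinstructed at study visits. The documents report no such withdrawal and give no expected rate. Exit exams normally yield CFS, VMR and OSI from one visit, the same measures are taken at Months 1 and 2, and the full analysis set keeps the patient. The SAP calls the study purely exploratory (6.4). An amendment has a cost, and because the SAP reports enrolment in the past tense, few patients may be left to benefit. All of this stands, and it makes the point a modest one. It does not remove it: an exit exam at Day 28 is not a Day 84 result, and 7.5 asks only for efforts.

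A reader might go further and infer that withdrawal removes the least improved patients, narrows the range of CFS change and pulls the primary correlation toward zero. Treating it as truncation of a normal distribution, loss of the lowest 12% (2 of 17) multiplies the SD by 0.825. A correlation of 0.50 then becomes 0.50 × 0.825 / √(1 − 0.25 + 0.25 × 0.825²) = 0.43. That is an extreme bound for deleted pairs. The primary analysis does not delete them, and nothing in the documents says that poor compliers are the worst responders.

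A reader might also infer that the full analysis set becomes nearly a per-protocol set. It does not: a patient withdrawn before Day 77 is in the former and out of the latter.

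**Conclusion.** The point holds as a small, avoidable loss of data. Poor dosing alone can end follow-up, and an exit before Day 77 then substitutes an earlier result for a valid Month 3 pair in the primary analysis and takes the patient out of the observed-only and per-protocol repeats. The comparison of full analysis set with per-protocol then partly reflects a carried-forward value and not only compliance.

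The cost in the repeats is about 0.02 to 0.04 of interval width per pair, assuming 17 pairs at the start and an absolute correlation of 0.5. That is modest beside the widening from 0.56 to 0.77 that comes from 17 patients where 30 were intended. A cut in the range of CFS change is not shown, and it is negligible if poor compliers resemble the vehicle patients. Vehicle at Month 6 is only a proxy for missed doses over three months. How often the rule would be used is unknown.

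**What to change.** In Protocol 8.2 and 9.2, state that persistent non-compliance with study medication is recorded as a deviation and that the patient is asked to remain for all scheduled assessments through Month 3 (Day 84 ± 7), unless consent is withdrawn or another listed withdrawal reason applies. Limit reason 8 of 7.4 in the same way, but only for non-compliance with study medication. Leave it unchanged for missed visits or procedures, where a Month 3 pair may not be obtainable anyway. Decisions about treatment itself stay as written.

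The visits are already in the schedule, so the cost is a short protocol amendment with its approval. The full analysis set would then hold observed Month 3 data from some poorly dosed patients. The per-protocol repeat can examine their influence, but only if the sponsor's review before database lock excludes them for compliance below 80%. SAP 5.3 does not make that exclusion automatic.
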